10. PARTICIPANT COMPLETION/DISCONTINUATION OF STUDY VACCINE/ WITHDRAWAL FROM THE STUDY

10.1. Completion

A participant will be considered to have completed study vaccination if he or she has received all vaccinations. A participant will be considered to have completed the study if he or she completed assessments at the final visit 24 months (Cohort 1 and Cohort 2 [Groups 11-13 and Groups 16-18]) or 36 months (Cohort 2 [Groups 14 and 15] and Cohort 3) after the first vaccination.

10.2. Discontinuation of Study Vaccine/Withdrawal from the Study

Discontinuation of Any Study Vaccine

A participant will not be automatically withdrawn from the study if he or she has to discontinue from study vaccination before the end of the study vaccine regimen.

Participants will be discontinued from vaccination for the reasons listed below. These participants must not receive any additional dose of any study vaccine but should continue to be monitored for safety and, if this does not result in safety risks for the participant, for immunogenicity (if the reason for discontinuation is not because of impaired functioning of the immune system) and/or other study procedures (eg, RTI follow-up). Additional unscheduled visits may be performed for safety/reactogenicity reasons, if needed.

In the event of questions, the investigator is encouraged to contact the sponsor:

- Anaphylactic reaction post vaccination, not attributable to causes other than vaccination
- An SAE or other potentially life-threatening (Grade 4) event that is determined to be related to study vaccine
- Any related AE, worsening of health status or intercurrent illness that, in the opinion of the investigator, requires study vaccine discontinuation
- Chronic or recurrent use of immunosuppressants (after discussion with the sponsor)
- Unblinding on the participant level that, in the opinion of the sponsor, would compromise the integrity of the data

Participants who miss a vaccination, not due to the reasons above, can receive subsequent vaccinations if, at the time of administration, the investigator determines that they are eligible to receive the vaccination according to the criteria in Section 10.3. In the event of questions, the investigator is encouraged to contact the sponsor.

Withdrawal from the Study

Each participant has the right to withdraw from the study at any time for any reason without affecting the right to treatment by the investigator. The investigator should make an attempt to contact participants who did not return for scheduled visits or follow-up. Although participants are

not obliged to give a reason for withdrawing prematurely, the investigator should make a reasonable effort to ascertain the reason(s) while fully respecting the participant's rights.

A participant will be withdrawn from the study for any of the following reasons:

- Lost to follow-up
- Withdrawal of consent
- Death
- Repeated failure to comply with protocol requirements
- Decision by sponsor, investigator, or local regulatory authorities and Institutional Review Board/Independent Ethics Committee (IRB/IEC)

If a participant is lost to follow-up, every reasonable effort must be made by the study-site personnel to contact the participant and determine the reason for discontinuation/withdrawal. The measures taken to follow-up must be documented.

When a participant withdraws before completing the study, the reason for withdrawal is to be documented in the eCRF and in the source document. Study vaccine assigned to the withdrawn participant may not be assigned to another participant. In general, participants who withdraw will not be replaced, unless the participant was randomized but did not receive any study vaccine.

In Cohort 1, any randomized participant withdrawn from the study for reasons other than (an) AE(s) after the first dose but before the second dose might be replaced at the discretion of the sponsor. In Cohort 2, no replacements or additional randomizations will be done for withdrawals after the first dose. In Cohort 3, if randomized participants are withdrawn from vaccination before the first dose of the selected regimen is administered, additional participants may be recruited to replace these participants at the discretion of the sponsor.

If a participant withdraws prematurely from the study, assessments for early withdrawal should be obtained (see also Section 9.1.8). Participants who wish to withdraw consent from participation in the study will be offered a single exit visit for safety follow-up (prior to formal withdrawal of consent). They have the right to refuse.

Withdrawal from the Use of Samples in Future Research

The participant may withdraw consent for use of samples for future research (see Section 16.2.5). In such a case, samples will be destroyed after they are no longer needed for the clinical study. Details of the sample retention for research are presented in the main ICF.

10.3. Contraindications to Vaccination

The following events constitute a contraindication to vaccination at that point in time. If any of these events occur at the scheduled time for vaccination, the participant may be vaccinated up to

10 days beyond the scheduled vaccination, or be withdrawn from vaccination at the discretion of the investigator and after consultation with the sponsor:

- Severe acute illness at the time of vaccination. This does not include minor illnesses such as diarrhea.
- Fever (body temperature ≥ 38.0 °C) at the planned time of vaccination.
- Medically-indicated vaccines should be given at least 14 days before or 14 days after study vaccine administration (see Section 8).

11. STATISTICAL METHODS

Statistical analysis will be done by the sponsor or under the authority of the sponsor. A general description of the statistical methods to be used to analyze the immunogenicity and safety data is outlined below. Specific details will be provided in the Statistical Analysis Plan.

Planned analyses are described in Section 11.6.

11.1. Analysis Sets

Vaccine assignment will follow the as-treated principle.

The Full Analysis (FA) Set will include all participants who were randomized and received at least one dose of vaccine (active or placebo), regardless of the occurrence of protocol deviations or the type of vaccine (ie, Ad26.RSV.preF, RSV preF protein, Ad26.RSV.preF/RSV preF protein combination or mixture). All safety and participant information analyses will be based on the FA set.

The Per-protocol RSV Immunogenicity (PPI) Set will include all participants who were randomized and received the complete first dose, and for whom immunogenicity data are available, excluding participants with major protocol deviations expecting to impact the immunogenicity outcomes.

In addition, the following samples will not be included in the PPI set:

- For participants who experience a natural RSV infection (based on RT-PCR, or other sources), samples collected after the natural infection will not be taken into account in the assessment of the immunogenicity of the selected regimen.
- If a participant misses one or more active dose(s) of the selected regimen but continues the planned visit schedule, samples after the missed active dose(s) will not be taken into account.

The analysis of all secondary and exploratory immunogenicity endpoints related to RSV will be based on the PPI set. Depending on the number of samples excluded, a post-hoc exploratory analysis might be performed, including the excluded samples. To visualize excluded samples, participant profiles from several assays might be repeated, indicating the excluded samples.

11.2. Sample Size Determination

11.2.1. Initial Safety Cohort (Cohort 1)

The number of participants chosen for the initial safety cohort will provide a preliminary safety assessment. Placebo recipients are included for blinding and safety purposes and will provide additional control specimens for immunogenicity assays.

While mild to moderate vaccine reactions (local injection site, systemic responses) are expected, AEs that preclude further vaccine administration or more serious ones that would limit product development are not anticipated.

Table 18 shows the probabilities of observing at least one AE in the initial safety cohort at given true AE rates. In the analysis of the initial safety cohort (Cohort 1), placebo recipients will be shown pooled.

Table 18: Probability of Observing at Least One Adverse Event in the Initial Safety Cohort (Cohort 1) at a Given True Adverse Event Rate

True Adverse Event Rate	Probability of Observing at Least One Adverse Event in N Participants		
	N=4	N=8	N=16
0.5%	2%	4%	8%
1%	4%	8%	15%
2.5%	10%	18%	33%
5%	19%	34%	56%
10%	34%	57%	81%
25%	68%	90%	99%
50%	94%	100%	100%

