If any of the pre-specified study vaccination pausing rules is met, further study vaccination will be paused and a DRC meeting will be convened.

The DRC may also review unblinded immunogenicity data during the course of the study if this is deemed necessary for future vaccine development-related decisions.

Initial Safety Cohort (Cohort 1)

In the initial safety cohort, participants will be randomized progressively in 1 of 4 randomizations (R1a through R1d) with safety checks in place before extending enrollment and progressing from one randomization step to the next as follows (Table 1):

- **Cohort R1a.** Initially 2 participants will be enrolled, 1 into Group 1 and 1 into Group 2, and will receive a single dose of placebo or 50 μg of RSV preF protein, respectively. Enrollment will be paused to allow for 24-hour safety assessments in these 2 sentinel participants by the principal investigator(s) (PI[s]), the sponsor's study responsible physician/scientist (SRP/S), and the sponsor's medical leader (ML). In the absence of any clinical safety concerns over the 24-hour assessment, the remaining 10 participants will be randomized and dosed. Seven days after the last participant has received his/her

first dose, available safety data will be reviewed by the PI(s), SRP/S, ML, and the sponsor's therapeutic area safety head (TASH) before proceeding to Cohort R1b.

- Cohort R1b. Initially 3 participants will be enrolled, 1 into each of Groups 3 through 5, and will receive a single dose of placebo, 5×10^{10} viral particles (vp) Ad26.RSV.preF/50 μ g RSV preF protein, or 150 μ g RSV preF protein, respectively. Enrollment will be paused to allow for 24-hour safety assessments in the 3 sentinel participants by the PI(s), SRP/S, and ML. In the absence of any clinical safety concerns over the 24-hour assessment, the remaining 17 participants will be randomized and dosed. Seven days after the last participant has received his/her first dose, available safety data will be reviewed by the PI(s), SRP/S, ML, and TASH before proceeding to Cohort R1c.

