- Cohort R1c. Initially 2 participants will be enrolled, 1 into Group 6 and 1 into Group 7, and will receive a single dose of placebo or 5×10^{10} vp Ad26.RSV.preF/150 μ g RSV preF protein, respectively. Enrollment will be paused to allow for 24-hour safety assessments in these 2 sentinel participants by the PI(s), SRP/S, and ML. In the absence of any clinical safety concerns over the 24-hour assessment, the remaining 10 participants will be randomized and dosed. Seven days after the last participant has received his/her first dose, available safety data will be reviewed by the PI(s), SRP/S, ML, and TASH before proceeding to Cohort R1d.
- Cohort R1d. Initially 3 participants will be enrolled, 1 into each of Groups 8 through 10, and will receive 2 doses of placebo (1 in each arm), or 1×10^{11} vp Ad26.RSV.preF/150 μ g RSV preF protein, with placebo in the opposite arm, or 1×10^{11} vp Ad26.RSV.preF in one arm and 150 μ g RSV preF protein in the opposite arm. Enrollment will be paused to allow 24-hour safety assessments in the 3 sentinel participants by the PI(s), SRP/S, and ML. In the absence of any clinical safety concerns over the 24-hour assessment, the remaining 17 participants will be randomized and dosed.
- Seven days after the final participant in Cohort 1 has received his/her first dose, all available safety data at that time for the whole cohort will be reviewed by the DRC before proceeding to Cohort 2.

Sentinel participants will be contacted by telephone 24 hours post-dose to collect safety information.

Progression to the regimen selection cohort will be based on acceptable safety in the initial safety cohort, as determined by DRC review of Day 8 safety data in all participants.

Table 1: Study Design: Initial Safety Cohort (Cohort 1)

Group	R	N	Day 1	Day 57	Month 12
1	R1a	4	Placebo	Placebo	Placebo
2	R1a	8	RSV preF protein 50 µg	RSV preF protein 50 µg	RSV preF protein 50 µg
3	R1b	4	Placebo	Placebo	Placebo
4	R1b	8	Ad26.RSV.preF/ RSV preF protein mixture: 5×10 ¹⁰ vp/50 µg	Ad26.RSV.preF/ RSV preF protein mixture: 5×10 ¹⁰ vp/50 µg	Ad26.RSV.preF/ RSV preF protein mixture: 5×10 ¹⁰ vp/50 µg
5	R1b	8	RSV preF protein 150 µg	RSV preF protein 150 µg	RSV preF protein 150 µg
6	R1c	4	Placebo	Placebo	Placebo
7	R1c	8	Ad26.RSV.preF/ RSV preF protein mixture: 5×10 ¹⁰ vp/150 µg	Ad26.RSV.preF/ RSV preF protein mixture: 5×10 ¹⁰ vp/150 µg	Ad26.RSV.preF/ RSV preF protein mixture: 5×10 ¹⁰ vp/150 µg
8	R1d	4	Placebo + Placebo*	Placebo	Placebo + Placebo*

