- Cohort R1b. Initially 3 participants will be enrolled, 1 into each of Groups 3 through 5, and will receive a single dose of placebo, 5×10^{10} vp Ad26.RSV.preF/50 µg RSV preF protein, or 150 µg RSV preF protein, respectively. Enrollment will be paused to allow for 24-hour safety assessments in the 3 sentinel participants by the PI(s), SRP/S, and ML. In the absence of any clinical safety concerns over the 24-hour assessment, the remaining 17 participants will be randomized and dosed. Seven days after the last participant has received his/her first dose,

available safety data will be reviewed by the PI(s), SRP/S, ML, and TASH before proceeding to Cohort R1c.

- Cohort R1c. Initially 2 participants will be enrolled, 1 into Group 6 and 1 into Group 7, and will receive a single dose of placebo or 5×10^{10} vp Ad26.RSV.preF/150 μ g RSV preF protein, respectively. Enrollment will be paused to allow for 24-hour safety assessments in these 2 sentinel participants by the PI(s), SRP/S, and ML. In the absence of any clinical safety concerns over the 24-hour assessment, the remaining 10 participants will be randomized and dosed. Seven days after the last participant has received his/her first dose, available safety data will be reviewed by the PI(s), SRP/S, ML, and TASH before proceeding to Cohort R1d.
- Cohort R1d. Initially 3 participants will be enrolled, 1 into each of Groups 8 through 10, and will receive 2 doses of placebo (1 in each arm), or 1×10^{11} vp Ad26.RSV.preF/150 μ g RSV preF protein, with placebo in the opposite arm, or 1×10^{11} vp Ad26.RSV.preF in one arm and 150 μ g RSV preF protein in the opposite arm. Enrollment will be paused to allow 24-hour safety assessments in the 3 sentinel participants by the PI(s), SRP/S, and ML. In the absence of any clinical safety concerns over the 24-hour assessment, the remaining 17 participants will be randomized and dosed.
- Seven days after the final participant in Cohort 1 has received his/her first dose, all available safety data at that time for the whole cohort will be reviewed by the DRC before proceeding to Cohort 2.

Sentinel participants will be contacted by telephone 24 hours post-vaccination to collect safety information.

Progression to the regimen selection cohort will be based on acceptable safety in the initial safety cohort, as determined by DRC review of Day 8 safety data in all participants.

Table 8: Study Design: Initial Safety Cohort (Cohort 1)

Group	R	N	Day 1	Day 57	Month 12

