Placebo controls will be used to establish the frequency and magnitude of changes in endpoints that may occur in the absence of active vaccine. Randomization will be used to minimize bias in the assignment of participants to vaccine groups, to increase the likelihood that known and unknown participant attributes (eg, demographics, baseline characteristics) are evenly balanced across vaccine groups, and to enhance the validity of statistical comparisons across vaccine groups. Blinded treatment will be used to reduce potential bias during data collection and evaluation of endpoints.

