5. TREATMENT ALLOCATION AND BLINDING

Study Vaccine Allocation

Central randomization will be implemented in this study. Participants will be randomly assigned to a vaccination group based on a computer-generated randomization schedule prepared before the study by or under the supervision of the sponsor. The randomization will be balanced by using randomly permuted blocks.

In the initial safety cohort (Cohort 1), the randomization ratio in Cohorts R1a and R1c is 1:2, in Cohorts R1b and R1d the ratio is 1:2:2. In each of those cohorts, 1 sentinel participant from each group (each active group and the placebo group to maintain the blind) will initially be enrolled to monitor for any unexpected severe adverse reaction. Therefore, the randomization will be phased to accommodate this and to end up with the overall randomization ratios specified above. No stratification will be applied.

In the regimen selection cohort (Cohort 2), the randomization ratio is 4:7:7:7:7:6:6:4. No stratification will be applied.

In the expanded safety cohort (Cohort 3), stratification will be applied: participants will be assigned to 1 of 2 strata prior to randomization, depending on the blood mononuclear cell (PBMC) sampling capability and capacity of the site. One stratum will contain a maximum of 63 participants from whom blood samples to assess humoral and cellular (PBMC samples) immunogenicity will be collected. The other stratum will contain the remaining participants, from whom blood samples will be collected only for humoral immunogenicity assessments, to reach the target of a total of 315 participants in Cohort 3. Within each stratum, participants will be randomized 3:3:1 ratio to one of the respective groups.

The interactive web response system (IWRS) will assign a unique code, which will dictate the group assignment for the participant. The requestor must use his or her own user identification and

personal identification number when contacting the IWRS, and will then give the relevant participant details to uniquely identify the participant.

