6. DOSAGE AND ADMINISTRATION

Ad26.RSV.preF and RSV preF protein will be administered either as a combination (as separate injections in opposite arms) or as a mixture (a single injection) into the deltoid muscle according to the schedules shown in Table 8, Table 9, Table 10 and Table 11:

- Ad26.RSV.preF (JNJ-64400141): will be supplied at a concentration of 2×10^{11} vp/1 mL in single-use vials. Dose levels of 5×10^{10} vp and 1×10^{11} vp will be used.
- RSV preF protein (JNJ-64213175): will be supplied at a concentration of 0.3 mg/1 mL in single use vials. Dose levels of 50 µg and 150 µg will be used.
- Placebo for Ad26.RSV.preF and RSV preF protein.

All injections of Ad26.RSV.preF and RSV preF protein (or corresponding placebo) will be 1 mL in volume.

An unblinded pharmacist, or other qualified individual, will prepare the appropriate vial and/or syringe and provide the syringe in a blinded manner to the vaccine administrator who will perform the injection. The unblinded pharmacist, or other qualified individual, may also perform vaccine administration, but will have no other study function following dosing. Diluent will be used as required.

Full details of vaccine preparation, including mixing of Ad26.RSV.preF and RSV preF protein, are provided in the Investigational Product Preparation Instructions.

All vaccines should be administered in the deltoid muscle:

- When participants receive 2 injections at any given visit, these injections will be given in opposite arms at the same time with no more than 45 minutes between the injections.
- When participants receive a single injection per visit, eg, in Groups 1 through 7 in Cohort 1, alternating injection sites will be used for subsequent injections unless there is a medically justifiable reason in the judgment of the PI(s).

No local or topical anesthetic should be used prior to the injection.

For each injection, a record should be made in the eCRF of which arm was injected.

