11.5. Safety Analyses

No formal statistical testing of safety data is planned. Per cohort, all safety data will be analyzed descriptively by regimen.

Adverse Events

The verbatim terms used in the eCRF by investigators to identify AEs will be coded using the Medical Dictionary for Regulatory Activities (MedDRA). All reported AEs with onset during the active phase (ie, AEs occurring after vaccination up to 28 days post-vaccination), and all SAEs will be included in the analysis. For each AE, the number and percentage of participants who experience at least one occurrence of the given event will be summarized by group.

Summaries, listings, datasets, or participant narratives may be provided, as appropriate, for those participants who die, who discontinue study vaccine due to an AE, or who experience a severe AE or an SAE.

Summaries and/or listings may be provided separately for AEs with onset outside the above defined timeframe (ie, beyond 28 days post-vaccination) and that were reported pre-dose at the time of subsequent vaccinations for studies using multiple doses.

Solicited local (at injection sites) and solicited systemic AEs will be summarized descriptively. The overall frequencies per vaccine group as well as frequencies according to severity and duration will be calculated for solicited AEs. In addition, the number and percentages of participants with at least one solicited local (at the injection site) or solicited systemic AE will be presented. Frequencies of unsolicited AEs, separately for all and vaccine-related only, will be presented by System Organ Class and Preferred Term.

Any RTI recorded as an AE in the eCRF that is subsequently determined to be RSV-positive by central laboratory RT-PCR will be excluded from the safety analysis and tabulated separately.

Clinical Laboratory Tests

For participants in Cohorts 1 and 2, laboratory abnormalities will be determined according to the FDA toxicity grading tables (see [Attachment 1](#)), or in accordance with the normal ranges for the clinical laboratory parameter if no grades are available. Any laboratory value shown as a “graded” value in the FDA table that is within central laboratory normal ranges will not be graded for severity.

Vital Signs

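### In Cohort 1, the participant-level row for any solicited local reaction compares two-injection Groups 9 and 10 with a pooled placebo column that is three-quarters single-injection

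*Protocol*

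**What the plan says.** **Pooling.** Protocol 11.2.1, next to Table 18: "In the analysis of the initial safety cohort (Cohort 1), placebo recipients will be shown pooled". It makes no exception for local reactions. The SAP does not mention placebo pooling.

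**Number of injections.** In the Cohort R1a step (Synopsis and Protocol 3.1.1), the placebo participant "will receive a single dose of placebo". Protocol 6 confirms the pattern for the early groups: "When participants receive a single injection per visit, eg, in Groups 1 through 7 in Cohort 1". In the R1d step, the Group 8 participant "will receive 2 doses of placebo (1 in each arm"). Table 8 shows Groups 8, 9 and 10 with two injections on Day 1, one on Day 57 and two at Month 12.

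**Reporting unit.** Protocol 11.5 promises that "the number and percentages of participants with at least one solicited local (at the injection site) or solicited systemic AE will be presented". SAP 5.1.2 also counts subjects, and SAP 5 uses the number of subjects as the denominator. SAP 5.1.1, however, says that when two arms are injected, local solicited events are recorded and reported arm by arm. SAP Attachment 2 then derives a single record for each event type, participant and post-dose period. It describes merging onsite and diary data and does not mention arm.

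**Purpose of placebo.** Protocol 3.2: "Placebo controls will be used to establish the frequency and magnitude of changes in endpoints that may occur in the absence of active vaccine".

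**The concern.** A participant with two injected arms has two opportunities to report a local reaction, and a participant with one arm has one. A percentage of participants with any local reaction is therefore comparable between columns only if the number of sites per person is similar.

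Group 8 was randomised with Groups 9 and 10 in R1d and has the same number of injections at each visit. Pooling dilutes it three to one with single-injection recipients. In the participant-level row, part of any excess in Groups 9 and 10 over placebo would then reflect only the second needle. The single-injection groups face a smaller error in the other direction. Reactogenicity is part of Cohort 1's primary objective, and Groups 9 and 10 carry its highest dose levels, so a reader is likely to make this comparison.

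**Working it through.** **Inputs**
- Placebo per group: 4 in each of Groups 1, 3, 6 and 8 (Table 8), so 16 in total. This agrees with the allocation in Protocol 5: "the randomization ratio in Cohorts R1a and R1c is 1:2, in Cohorts R1b and R1d the ratio is 1:2:2".
- Day 1 and Month 12: 12 placebo recipients with one injection (Groups 1, 3, 6) and 4 with two (Group 8).
- Day 57: all 16 with one injection.
- Groups 9 and 10: 8 participants each, with two injections on Day 1 and at Month 12.
- Placebo local-reaction rate per site (p) and between-arm correlation (r): not in the documents. Both are assumed and shown as ranges.

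**The plan's own figures.** Table 18 is 1-(1-q)^N, with q the true event rate. For N = 16 this gives 7.71%, 14.85%, 33.31%, 55.99%, 81.47%, 99.0% and 100.0% at q = 0.5%, 1%, 2.5%, 5%, 10%, 25% and 50%. The printed values are 8, 15, 33, 56, 81, 99 and 100. The N = 4 and N = 8 columns reproduce as well. The table is correct, but it assumes one common rate per participant. For local reactions on Day 1 and at Month 12, the 16 pooled recipients do not share one.

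**Effect of pooling on the participant-level row**
- One injection: p.
- Two injections: p + p(1-p)(1-r).
- Pooled placebo: [12p + 4(p + p(1-p)(1-r))]/16 = p + 0.25p(1-p)(1-r).
- Shortfall for two-injection groups: 0.75p(1-p)(1-r).
- Excess for single-injection groups: 0.25p(1-p)(1-r).

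| p | Pooled, r = 0 | Two injections, r = 0 | Shortfall, r = 0 | r = 0.5 | r = 1 |
|---|---|---|---|---|---|
| 10% | 12.25% | 19.0% | 6.75 points | 3.4 | 0 |
| 20% | 24.0% | 36.0% | 12.0 points | 6.0 | 0 |
| 30% | 35.25% | 51.0% | 15.75 points | 7.9 | 0 |

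At r = 0 the shortfall is 3.6 points at p = 5% and reaches its maximum of 18.75 points at p = 50%. The excess for single-injection groups at r = 0 is 2.25, 4.0 and 5.25 points at p = 10%, 20% and 30%.

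**Where the shortfall is zero**
- Tables by arm: the expected placebo rate per injection is p, whether a person had one injection or two.
- Day 57: every Cohort 1 group gets one injection.

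**Precision, for scale.** An observed 2/16 has an exact 95% CI of 1.6% to 38.3%. Group 8 alone with 1/4 has 0.6% to 80.6%.

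**The case against.** The strongest reply is that the SAP already solves this. SAP 5.1.1 reports two-arm local events arm by arm, and Protocol 11 leaves details to the SAP. For those tables the reply is right. It does not remove the participant-level percentage in Protocol 11.5, and Attachment 2, read literally, merges the two arms into one record. Neither document says how Group 8's two arms enter the pooled column.

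The second reply is that nothing stated depends on the comparison, and this also stands. SAP 5 rules out formal group comparisons. The only pausing rule on solicited events (rule 4) covers systemic ones. Solicited local events are related by definition. Progression rests on safety review, not on a stated excess over placebo.

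Third, Cohort 2 has a matched control: its placebo Group 18 (n=24) gets two Day 1 injections, as does every other Cohort 2 group. Groups 14 and 17 repeat Group 9's Day 1 treatment, and Group 16 repeats Group 10's. The problem is thus confined to small Cohort 1 groups, though Cohort 2 has no Month 12 booster.

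Fourth, independence between arms is a high-end assumption, because reactions in one person are probably positively correlated. Fifth, replacing the pool with a column of 4 would exchange a modest bias for almost no information. Both points stand and shape the fix.

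**Conclusion.** The point holds as a minor one, limited to a single row at two vaccinations. On Day 1 and at Month 12, the pooled placebo percentage with any solicited local event is too low a background for Groups 9 and 10 by 0.75p(1-p)(1-r). That is 6.8 to 15.8 points for p of 10% to 30% at r = 0, half that at r = 0.5 and nothing at r = 1. These sizes rest on assumed values of p and r. Only the 12/4 split and the direction (for r below 1) come from the documents. At this sample size, sampling error is often larger than the bias, but the bias is systematic, known in advance and removable.

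A reader might infer that Cohort 1's background local-reaction rate is understated generally, or that the decision to proceed to Cohort 2 is distorted. The documents support neither: by-arm tables and Day 57 carry no such error, the analysis is descriptive, and no stated rule uses the contrast. Nor are any placebo data missing, since every injection given is observed.

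**What to change.** - **SAP 5.1.1, 5.1.5 and Attachment 2:** keep arm as a level in the solicited local event records, and say whether each local row is per arm or per participant. This settles the conflict between reporting by arm and one record per participant.
- **Day 1 and Month 12, every group:** add a rate per injection site. Pooled placebo has 20 sites (12 x 1 + 4 x 2), and Groups 9 and 10 have 16 each (8 x 2). Group 9's 16 sites are 8 mixture and 8 placebo, so its arms should also be readable separately.
- **Participant-level row, Day 1 and Month 12:** keep the pooled n=16 column and also show it split by number of injections (n=12 and n=4). Add a note that the n=4 column is very imprecise, with the 1/4 interval above as illustration.
- **Leave the pool unchanged** for systemic solicited events, unsolicited events, SAEs and Day 57.

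The cost is SAP wording, a few table rows and one imprecise column. No new data or change in conduct is needed.
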